7.7 Safety Follow-up

7.7.1 Telephone Call (Week 10)

Subjects will receive a TC from the study site approximately 2 weeks after the last dose of study drug to inquire about AEs and concomitant medication usage, and will administer the C-SSRS.

7.7.2 Ocular Examination (Week 12)

The final ocular examination for corneal specular microscopy is to be conducted approximately 12 weeks (+2 days) after the first dose of study drug (including both subjects who complete the study and subjects who discontinue early from the study); exceptions to be discussed with medical monitor.

Additional ophthalmologic examinations (standard ophthalmologic exams and/or corneal specular microscopies) may be conducted to monitor subject safety.

8 SAFETY MONITORING AND REPORTING

Investigators are responsible for the detection and documentation of events that meet the definition of an AE, an SAE, suspected adverse reaction, serious suspected adverse reaction, unanticipated problems, or AESIs, as provided in this protocol.

Investigators must review the BTRX-335140 IB to be aware of the safety-related events, which may be anticipated with its use. Investigators will also be versed in the latest standard of care guidelines.

8.1 Adverse Events

8.1.1 Definition of an Adverse Event

An AE is defined as any untoward medical occurrence associated with the use of a drug in humans, whether or not considered drug related.

An AE may be any unfavorable and unintended sign, symptom, illness, clinically significant abnormal laboratory value or ECG finding, or other untoward medical occurrence that appears or worsens in a subject during a clinical study. This definition does not imply a causal relationship between the AE and the study drug.

Adverse events beginning with the initial dose of study drug or during the subsequent duration of their enrollment in the study will be considered TEAEs. Treatment-emergent AEs will be recorded on the AE eCRF to include the event, date of onset, whether the AE is associated with an episode of self-harm, severity, frequency, seriousness, date of resolution, action taken with respect to the AE (eg, discontinue study drug, begin concomitant medication, begin nonpharmacological treatment, etc.), outcome, and relationship to the study drug. All TEAEs related to study drug will be followed to a satisfactory resolution or until the event becomes stable or can be explained by another known cause (ie, concurrent condition or medication).

Medical conditions present or AEs occurring prior to the first dose of study drug will be captured as medical history in the eCRF. Any AE occurring during the study that is related to a pre-existing condition or event that worsens in intensity or frequency after the first dose of study drug will be recorded as a TEAE.

Lack of drug effect is not an AE in clinical studies because the purpose of the clinical study is to establish drug effect.

8.1.2 Definition of a Serious Adverse Event

Serious AEs will be recorded on the AE eCRF from the time of informed consent. An SAE is any AE that results in 1 of the following outcomes, regardless of the investigator's opinion of causation:

- Death
- Initial or prolonged inpatient hospitalization

BTRX-335140	BlackThorn Therapeutics, Inc.
Clinical Study Protocol Amendment 7	Date: 24Jan2022

- Surgeries planned prior to signing the ICF will not be considered SAEs. However, worsening of the underlying medical condition during the study will be considered an AE and must be captured as serious if any SAE-defining outcomes occur as a result.
- A life-threatening experience (that is, immediate risk of dying)
- Persistent or significant disability/incapacity
- Congenital anomaly/birth defect
- Other medically important serious event as determined by the investigator (for example, an AE that jeopardizes the subject and may require medical or surgical intervention to prevent 1 of the outcomes listed in this definition)

The following events do not meet the definition of an SAE:

- Hospitalization for elective treatment of a pre-existing condition that does not worsen from baseline
- Hospitalizations for a standard procedure for study drug administration and routine monitoring of the studied indication not associated with any deterioration in condition
- Social or convenience admission to a hospital
- Prolongation of a hospitalization for social or convenience reasons not associated with the occurrence of an AE
- Hospitalization or an emergency room visit that lasts less than 24 hours that does not meet the criteria of an important medical or a life-threatening event

8.1.3 Definition of Suspected Adverse Reaction

A suspected adverse reaction is defined as any AE for which there is a reasonable possibility that the AE was caused by the study drug.

8.1.4 Definition of Serious Suspected Adverse Reaction

A serious suspected adverse reaction is any suspected adverse reaction that is determined to be serious, based on the definition of an SAE in Section 8.1.2.

8.2 Classification of Adverse Events

8.2.1 Severity of Adverse Events

The investigator will assess the severity of each AE based on his/her clinical judgment using one of the following categories:

BTRX-335140	BlackThorn Therapeutics, Inc.
Clinical Study Protocol Amendment 7	Date: 24Jan2022

- Mild: Usually transient and may require only minimal treatment or therapeutic intervention. The event does not generally interfere with usual activities of daily living.
- **Moderate:** Usually alleviated with additional specific therapeutic intervention. The event interferes with usual activities of daily living, causing discomfort but poses no significant or permanent risk of harm to the subject.
- Severe: Interrupts usual activities of daily living, or significantly affects clinical status, or may require intensive therapeutic intervention.

8.2.2 Relationship to Study Drug

The investigator will assess the relationship (ie, causality) of each AE to study drug based on his/her clinical judgment. The investigator's assessment of an AE's relationship to study drug is part of the documentation process, but it is not a factor in determining what is or is not reported in the study. If there is any doubt as to whether a clinical observation is an AE, the event should be reported. All AEs must have their relationship to study agent assessed. The Sponsor's assessment of relationship may differ from the investigator's assessment.

Relationship to study drug will be assessed according to the following guidelines:

- **Possibly related:** The AE is known to occur with the study drug, there is a reasonable possibility that the study drug caused the AE, or there is a temporal relationship between the study drug and event. Reasonable possibility means that there is evidence to suggest a causal relationship between the study drug and the AE.
- Unlikely related: There is not a reasonable possibility that the administration of the study drug caused the event, there is no temporal relationship between the study drug and event onset, or an alternate etiology has been established.

For initially reporting SAEs, even in situations in which minimal information is available, it is important that the investigator make an assessment of causality for every event. The causality assessment is 1 of the criteria used when determining regulatory reporting requirements. The investigator may change his or her opinion of causality in light of follow-up information and amend the SAE information accordingly in the eCRF or the SAE reporting form, as applicable.

8.3 Time Period and Frequency for Event Assessment and Follow-up

All AEs from the time of informed consent through the last follow-up visit will be recorded in each enrolled subject's eCRF (see Section 6.3.1). For subjects who prematurely discontinue from the study, AEs will continue to be recorded through the last follow-up visit. For subjects who are found to be ineligible for the study during the Screening period and are not enrolled (ie, Screening failures), AEs that are SAEs will be captured. Adverse events beginning with the initial dose of study drug or during the subsequent duration of their enrollment in the study will be considered TEAEs. Treatment-emergent AEs will be recorded on the AE eCRF to include the event, date of onset, whether the AE is associated with an episode of self-harm, severity, frequency, seriousness, date of resolution, action taken with respect to the AE (eg, discontinue study drug, begin concomitant medication, begin

BTRX-335140	BlackThorn Therapeutics, Inc.
Clinical Study Protocol Amendment 7	Date: 24Jan2022

nonpharmacological treatment, etc.), outcome, and relationship to the study drug. All TEAEs related to study drug will be followed to a satisfactory resolution or until the event becomes stable or can be explained by another known cause (ie, concurrent condition or medication).

• All SAEs that occur after the informed consent is signed will be captured. Serious AEs reported after a subject has taken the last dose of study drug will be collected in the pharmacovigilance system for 30 days after the last dose of study drug. Thereafter, only SAEs that the investigator feels were related to the study drug or a protocol procedure must be reported.

8.4 Adverse Events of Special Interest

Adverse events of special interest (serious or nonserious) are TEAEs of particular safety importance and are required to be reported to the sponsor immediately (and no more than 24 hours after learning of the event, see Section 8.5 for reporting requirements).

Adverse events of special interest for this study are based on nonclinical findings of skin-related and ocular phototoxicity (see Section 1.1.3). Reported TEAEs that are classified in the system organ classes (SOCs) listed below will be considered AESIs:

- Skin and subcutaneous tissue disorders
- Eye disorders

Nonserious AEs in the above SOCs that occur prior to study drug dosing will be recorded in medical history.

Investigators will monitor for dermatologic or ocular events and for any change in visual acuity.

8.5 **Reporting Procedures**

8.5.1 Reporting Serious Adverse Events and Adverse Events of Special Interest

All SAEs and AESIs must be reported on a study-specific SAE/AESI form in addition to the AE eCRF by electronic data capture (EDC). Study site personnel must alert the Sponsor-designated medical monitor of the SAE/AESI and must submit the completed study-specific SAE/AESI form to

within 24 hours of the site's awareness of the

SAE/AESI.

The investigator must also enter the SAE/AESI information into the eCRF as soon as possible thereafter.

In the initial email, the investigator must provide to the Sponsor the SAE/AESI form, completed to the greatest extent possible and the following pages from the eCRF:

• AE record

BTRX-335140	BlackThorn Therapeutics, Inc.
Clinical Study Protocol Amendment 7	Date: 24Jan2022

- Medical history
- Prior and concomitant medications

Also, the following documents are to be forwarded: any laboratory results, diagnostic test results, or medical reports relevant to the SAE/AESI.

The investigator and supporting personnel responsible for subject care should discuss with the Sponsor-designated medical monitor or designee any need for supplemental investigations of SAEs/AESIs. The results of these additional assessments conducted must be reported to the Sponsor-designated medical monitor.

In the event of a medical emergency in which knowledge of the subject's treatment assignment may influence their clinical care the investigator has the option to unblind the subjects' treatment assignment via the IWRS system. The investigator should make every effort to contact the medical monitor prior to unblinding unless this would adversely delay appropriate medical care. The medical monitor will not be unblinded, they will only provide assistance to the investigator. The reasons for unblinding must be noted in the source documents. The investigator must not disclose the subject's treatment assignment to anyone who does not need the information due to their direct involvement in the subject's clinical care. Disposition of subjects who are unblinded due to a medical emergency will be determined following discussion with the Sponsor.

In the event of death, every effort should be made to obtain a death certificate and if possible, an autopsy report. If the cause of death is unknown, death will be recorded as the event.

The investigator is responsible for safety reporting in compliance with their IRB.

8.5.2 *Regulatory Reporting Requirements*

The investigator must promptly report all SAEs to the Sponsor in accordance with the procedures detailed in Section 8.5.1. The Sponsor has a legal responsibility to notify, as appropriate, both the local regulatory authority and other regulatory agencies about the safety of a product under clinical investigation. Prompt notification of SAEs by the investigator to the appropriate project contact for SAE receipt is essential so that serious suspected adverse reactions that are either unexpected or observed with increasing occurrence be reported and legal obligations and ethical responsibilities regarding the safety of other subjects are met.

Investigator letters are prepared according to Sponsor policy and are forwarded to the investigators as necessary. An investigator letter is prepared for a serious unexpected suspected adverse reaction (SUSAR) that is attributable to study drug. The purpose of the investigator letter is to fulfill specific regulatory and cGCP requirements regarding the product under investigation.

The investigator, or responsible person according to local requirements, must comply with requirements related to the reporting of SAEs to the IRB.

Confidential

BTRX-335140	BlackThorn Therapeutics, Inc.
Clinical Study Protocol Amendment 7	Date: 24Jan2022

The Sponsor is responsible for informing IRB, investigators, and regulatory authorities of any finding that could adversely affect the safety of subjects or affect the conduct of the study. Events will be reported to regulatory authorities in accordance with expedited reporting requirements.

8.5.3 Overdose

Overdose is defined as an accidental or intentional administration of more than the intended dose of study drug. In the event of an overdose of study drug, the investigator should use clinical judgment in treating the overdose and contact the Sponsor-designated medical monitor, or designee. The investigator should refer to the relevant document(s) for detailed information regarding warnings, precautions, contraindications, AEs, and other significant data pertaining to the study drug. Such documentation may include, but not be limited to the IB.

8.5.4 Pregnancy Reporting

If a female subject or the female partner of a treated male subject becomes pregnant, the subject must notify the investigator within 24 hours of learning of the pregnancy. The investigator must make every effort to ensure that the subject or the pregnant female is aware of the need to notify her healthcare provider regarding her male partner's participation in this clinical study and his potential exposure to BTRX-335140.

The study site must complete a pregnancy form and send to the Sponsor or designee within 24 hours of learning of the pregnancy. The study site will make every effort to follow the pregnancy until outcome is known.

8.6 Safety Oversight

The Sponsor-designated medical monitor and the study team will monitor blinded safety data throughout the course of the study as detailed in the medical monitoring plan. This will include review of AEs, SAEs, AESIs, ECG findings, clinical laboratory results, vital signs, ophthalmologic findings, and other safety data.

In the event that safety monitoring uncovers an issue that needs to be addressed by unblinding at the group level, a data monitoring committee will be formed to protect the integrity of data and to evaluate additional analyses of the safety data.

BTRX-335140	BlackThorn Therapeutics, Inc.
Clinical Study Protocol Amendment 7	Date: 24Jan2022

9 STATISTICAL CONSIDERATIONS

9.1 General Considerations

Full details on the statistical methodology to be used will be included in a statistical analysis plan (SAP) to be developed prior to study unblinding.

For the purpose of all safety analyses where applicable, baseline is defined as the last measurement prior to the start of study drug administration. For efficacy analyses, baseline is defined as the arithmetic mean of pretreatment measurements ie, Screening and Baseline, prior to the first administration of study drug, or as the last measurement prior to the first administration of study drug if only single value is available.

Continuous endpoints will be summarized with n, mean, standard deviation (SD), median, minimum and maximum. In addition, change from baseline and percent change from baseline values will be calculated at each time point and summarized descriptively. For categorical endpoints, descriptive summaries will include counts and percentages.

No adjustments will be made for multiple comparisons.

All statistical comparisons will be 2-sided with alpha of 0.05.

SAS version 9.4 or higher will be used to analyze data.

9.2 Analysis Populations

The safety analysis will be conducted on the Safety Population. Efficacy analyses will be conducted on the Efficacy population and the per-protocol (PP) population. The Efficacy population will be used for the primary efficacy analysis.

Subjects will be analyzed according to randomized treatment assignment for efficacy assessments and according to treatment received for safety assessments.

9.2.1 Safety Population

The Safety population is defined as all subjects who received study drug and will be used to summarize safety data.

9.2.2 Efficacy Population

The Efficacy population includes all randomized subjects who received at least 1 dose of study drug, have a baseline HAMD-17 assessment value, and have at least 1 post-baseline assessment. This population will be used to summarize the primary and other efficacy data.

9.2.3 Per-protocol Population

The PP population includes subjects in the efficacy population who did not experience any major protocol deviations that impact primary efficacy endpoint analysis.

BTRX-335140	BlackThorn Therapeutics, Inc.
Clinical Study Protocol Amendment 7	Date: 24Jan2022
9.2.4	

9.3 Statistical Analysis Methods

9.3.1 Disposition

Frequency counts and percentages of subjects who were screened, randomized, completed the treatment, or discontinued early will be presented by treatment group. Reasons for discontinuation will be summarized.

9.3.2 Demographics and Baseline Characteristics

Demographic and baseline characteristics including age, sex, BMI, race, ethnicity, height, weight, CGI-S, baseline HAMD-17, duration of current depressive episode, antidepressant treatment during the current episode, and other medical history, physical examinations, and prior and concomitant medications will be summarized using descriptive statistics. Prior and concomitant medications will be summarized by World Health Organization Drug Classification (WHODrug) for Drug Statistics Methodology.

9.3.3 *Efficacy Analyses*

9.3.3.1 Primary Efficacy Analysis

The primary efficacy analysis is a comparison of mean reduction in HAMD-17 scores between BTRX-335140 and placebo at Week 8. The analysis will be conducted using a Mixed-Models Repeated Measures (MMRM) with change from baseline in HAMD-17 score as the dependent variable and will include treatment group, Week, and Week by treatment group interaction as factors, and baseline HAMD-17 score as covariate. Variance estimation will be based on an unstructured covariance matrix. The model-based Week 8 least square (LS) means, standard errors, 95% confidence intervals (CIs), and *p*-values will be reported.

9.3.3.2 Secondary Efficacy Analyses

Similar to the method described above, a MMRM model will be calculated for the change from baseline to each timepoint assessed for comparisons between BTRX-335140 and placebo for the measures listed below. The model-based time points' LS means, standard errors, 95% CIs, and *p*-values will be reported. Alternatively, ANCOVA may be used, as appropriate. The following measures will be analyzed:

- CGI-I
- CGI-S
- SHAPS
- HADS subscales: HADS-A and HADS-D

BTRX-335140	
Clinical Study Protocol Amendment 7	

- HAM-A total score
- SDS

For CGI-I, an additional analysis comparing the percentage of subjects with responses at Week 4 and Week 8 of 'much improved' or 'very much improved' between BTRX-335140 and placebo will be performed using generalized estimating equations (GEE). The model will include treatment, baseline CGI-S score, week, and week by treatment group interaction. An exchangeable working correlation structure will be assumed.

The change from baseline to Week 8 in CGI-S will be estimated using an ANCOVA model, with main effects for treatment group and a covariate adjustment for baseline score.

The response rates (the percentage of subjects with \geq 50% decrease in HAMD-17 from baseline to Week 4 and Week 8) will be compared between BTRX-335140 and placebo-treated groups using Cochran-Mantel-Haenszel test. Additional categories may be explored.

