4.2 Method of Assigning Subjects to Treatment

Subjects who meet all inclusion criteria and are subsequently not excluded by the exclusion criteria will be randomized to double-blind treatment at Visit 2 (Baseline) using an interactive web-response system (IWRS). Subjects will be randomized in a 1:1 ratio to 1 of 2 treatment arms (placebo or BTRX-335140 QD).

The IWRS will be used to assign bottles containing double-blind study drug or placebo to each subject. Further details will be provided in the Pharmacy manual.

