6.3.2 Method of Assigning Subjects to Treatment Groups

Subjects who meet all inclusion criteria and are not excluded by the exclusion criteria are randomized to double-blind treatment at Visit 2 (Baseline) using an interactive web-response system (IWRS). Subjects are randomized in a 1:1 ratio to 1 of 2 treatment arms (placebo or BTRX-335140 QD).

The IWRS is used to assign bottles containing double-blind study drug or placebo to each subject. Further details are provided in the Pharmacy manual.

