6.4.1.2 Secondary Efficacy Variables

Secondary efficacy endpoints include the following:

- HAMD-17 response rate at Week 4 and Week 8. The response rate is the percentage of subjects with \geq 50% decrease from baseline in HAMD-17 score.
- CGI-I. CGI-I score assessed at each postbaseline timepoint compared to baseline. The CGI-I scale (Guy 1976) is a clinician-rated instrument that measures the improvement of the subject's symptoms. It is a 7-point scale where a score of 1 indicates that the subject is "very much improved," a score of 4 indicates that the subject has experienced "no change," and a score of 7 indicates that the subject is "very much worse." For analysis purposes, a CGI-I response indicating symptom improvement will be defined as "much improved" or "very much improved".
- SHAPS. Change from baseline to each timepoint assessed in SHAPS scores. The SHAPS is a 14-item self-report instrument which measures anhedonia (Snaith et al 1995). Each of the 14 items has a set of 4 responses, 2 of which endorse agreement (Definitely/Strongly Agree, Agree) and 2 of which endorse disagreement (Disagree, Strongly Disagree). There are two scoring methods.
 - SHAPS Original Total Score (0 to 14): The original method assigned a score of 1 to either of the disagreement responses (Disagree, Strongly Disagree) and a score of 0 to either of the agreement responses (Definitely/Strongly Agree, Agree). Therefore, original scores on the SHAPS can range from 0-14 with higher scores corresponding to higher levels of anhedonia.
 - SHAPS Total Score (14 to 56): The second method derives a total score by summing the item responses where Definitely/Strongly Agree responses score 1 point, Agree responses score 2 points, Disagree responses score 3 points, and Strongly Disagree responses score 4 points. Therefore, scores on the SHAPS can range from 14 to 56 by the second method, with higher scores corresponding to higher levels of anhedonia. Both methods will be used for analyses.

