7.4.6 Subgroup Analyses of the Primary Efficacy Endpoint

The primary efficacy endpoint (change from baseline to Week 8 in HAMD-17 total score) will be summarized using the following subgroups:

- Gender (male and female)
- Baseline HAMD-17 scores: $< 22 \text{ vs} \ge 22$
- by baseline SHAPS Total Score (14 to 56) (< median and ≥ median) and SHAPS Original Total Score (0 to 14) (< median and ≥ median).

Summaries by subgroup will only be produced if there are at least 20 subjects in the category of interest. Additional subgroup analyses may be performed post-hoc, as appropriate.

The primary endpoint (HAMD-17 total score) will also be summarized in subgroups of the Efficacy Population that include all subjects screened on or before March 16, 2020 (labeled as PreCOVID) versus the subjects screened after March 16, 2020 (labeled as PostCOVID).

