7.4.7 Secondary Endpoint Analysis Methods

Secondary endpoints including the change from baseline to each timepoint assessed for comparisons between BTRX-335140 and placebo for the measures listed below, will be analyzed using an MMRM model for treatment group, week, and week by treatment group interaction as fixed factors and a covariate adjustment for baseline score. For CGI-I, the baseline CGI-I score will not be included as a covariate, as the baseline assessment of CGI-I refers to the comparison with screening visit. For all other measures the baseline score included as a covariate will be the baseline score for that measure. Variance estimation will be based on an unstructured covariance matrix unless there is a lack of convergence in which case a heterogeneous autoregressive variance-covariance structure will be used.

- CGI-I at each post-baseline visit
- Change in SHAPS from baseline at each post-baseline visit
- Change in HADS total score and HADS subscales: HADS-A and HADS-D from baseline at each post-baseline visit
- Change in HAM-A total score from baseline at each post-baseline visit
- Change in SDS from baseline at each post-baseline visit

The response rates (the percentage of subjects with \geq 50% decrease in HAMD-17 from baseline to Week 4 and Week 8) will be compared between BTRX-335140 and placebotreated groups. The response rates, response rate difference and corresponding 95% Wald CI, and Cochran-Mantel-Haenszel p-value will be reported.

The change at Week 8 from baseline in CGI-S will be estimated using an analysis of the covariance (ANCOVA) model with main effects for treatment group and a covariate adjustment for baseline CGI-S score. The model-based LS means, standard errors, 95% CIs, and 2-sided p-values will be reported.

For SDS, analysis will be performed for the three SDS items separately and the SDS total score as the sum of the individual domains. Note that the work/school domain may be not applicable for all subjects and therefore the analysis of SDS total score will be performed for the subjects with all 3 domain scores and the checkbox of "No work or school" is NOT marked. In addition, a sensitivity analysis of SDS total score will be conducted for all subjects, where the SDS total score will be calculated as (sum of social and family life)*30/20 for the subjects for whom the checkbox of "No work or school" is marked.

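### The HAMD-17 response test names no stratum; stratifying it by baseline HAMD-17 is a free but small improvement, not the repair of an error

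*Protocol*

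**What the plan says.** Protocol Section 9.3.3.2: response rates at Weeks 4 and 8 "will be compared between BTRX-335140 and placebo-treated groups using Cochran-Mantel-Haenszel test". SAP Section 7.4.7: "The response rates, response rate difference and corresponding 95% Wald CI, and Cochran-Mantel-Haenszel p-value will be reported". No stratum or covariate is named in either place, and the SAP addendum adds none. SAP Section 6.4.1.2 defines the endpoint: "The response rate is the percentage of subjects with" a fall of at least 50% from baseline.

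Allocation is described without a stratification factor in Protocol Section 4.2 ("Subjects will be randomized in a 1:1 ratio to 1 of 2 treatment arms") and in SAP Section 6.3.2 ("Subjects are randomized in a 1:1 ratio to 1 of 2 treatment arms").

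Elsewhere the plan does use baseline scores:

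- The primary MMRM has baseline HAMD-17 as a covariate (Protocol 9.3.3.1, SAP 7.4.4).
- The CGI-S ANCOVA has baseline CGI-S (Protocol 9.3.3.2, SAP 7.4.7).
- The protocol's GEE for CGI-I response is adjusted: "The model will include treatment, baseline CGI-S score, week, and week by treatment group interaction".
- SAP Section 7.4.6 lists "Baseline HAMD-17 scores" cut at <22 v ≥22, as a subgroup of the primary endpoint only.

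The SAP's Efficacy population (Section 7.2) requires a baseline HAMD-17 total score, so the value is never missing in this analysis.

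**The concern.** A CMH test exists to combine strata. With none, it is the ordinary Pearson chi-square multiplied by (N-1)/N. The primary analysis of HAMD-17 corrects for chance differences between arms in baseline severity, while the response analysis of the same scale does not. With no stratified randomization described, such differences are limited only by chance. At stake are some power on a secondary endpoint and a response estimate that carries whatever baseline imbalance the trial happens to have. Naming CMH without a stratum also leaves the computation of the p-value open.

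**Working it through.** **1. Inputs.** From the documents: about 180 subjects randomized 1:1, so 90 per arm; two-sided alpha 0.05; response at ≥50% decrease; the cut at 22. Assumed, because the documents do not give them: baseline mean 22.5 and SD 3.5, residual SD 7, true difference 3 points, response about 35% v 51%, slope of change on baseline from 0 to -1.

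**2. The plan's own figure.** No power is stated for response. The 84% in the protocol's Summary of Changes belongs to the primary endpoint, and its effect size and SD are not in the readable text, so it cannot be reproduced. Back-solved at 90 per arm, it implies delta/SD = (1.960 + 0.994)/√(90/2) = 2.954/6.708 = 0.44. The assumed 3/7 = 0.43 is close to this.

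**3. Validity.** At N = 180 the unstratified CMH is the chi-square times 179/180 = 0.994. Simulated type I error was about 4 to 5.5% for the crude CMH, the stratified CMH and logistic regression with baseline.

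**4. How far response depends on baseline.** Write change = constant + slope × baseline + error. A subject responds when change ≤ -0.5 × baseline, that is when constant + (slope + 0.5) × baseline + error ≤ 0. The dependence is therefore proportional to (slope + 0.5). It vanishes at slope -0.5 and changes sign on either side.

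**5. Effect of chance imbalance.**

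- SD of the arm difference in mean baseline: 3.5 × √(2/90) = 0.52 points.
- Shift in response per baseline point: |slope + 0.5| × 0.370/7, where 0.370 is the normal density at the 35% point. At slope 0 or -1 this is 0.5 × 0.370/7 = 2.6 percentage points.
- Shift for a 1-SD imbalance: 2.6 × 0.52 = 1.4 percentage points at either end, in opposite directions, and 0 at slope -0.5.
- Standard error of the crude rate difference: √(0.35 × 0.65/90 + 0.51 × 0.49/90) = 0.073. The largest shift is 1.4/7.3 = 0.19 standard errors.

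**6. Power (20,000 simulated trials per row).**

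| Slope | Crude CMH | CMH stratified at 22 | Gain (points) | Gain minus the 0.5 at slope -0.5 |
|---|---|---|---|---|
| 0 | 58.8% | 60.5% | 1.7 | 1.2 |
| -0.25 | 60.4% | 61.4% | 1.0 | 0.5 |
| -0.5 | 60.9% | 61.4% | 0.5 | 0 |
| -0.75 | 60.8% | 61.7% | 0.9 | 0.4 |
| -1 | 58.4% | 60.3% | 1.9 | 1.4 |

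At slope -0.5 baseline carries no information about response, so the 0.5 there is not precision gained from baseline. It most likely reflects the discreteness of a single 2×2 table. A repeat run gave gains of 0.8 to 1.8 points, about 0.8 of which remained at slope -0.5, and a variance ratio (stratified to crude rate difference) of 0.98 to 1.00.

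**7. Sensitivity.** A second simulation (4,000 trials per scenario) fixed the Week 8 SD at 7 and delta/SD at 0.44, with baseline SD 3 or 4, and varied the baseline-to-Week 8 correlation.

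| Correlation | Stratified-CMH gain (points) |
|---|---|
| 0 | 2.3 to 2.8 |
| 0.2 | 1.1 to 1.4 |
| 0.4 | 0 to 2.2 |
| 0.6 | 4.2 to 5.5 |

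The last row lies outside the slope range used above. It implies a slope of change on baseline of 0.6 × 7/4 - 1 = +0.05 (SD 4) or 0.6 × 7/3 - 1 = +0.40 (SD 3), so that sicker subjects improve less in points.

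**The case against.** The strongest reply is that nothing here is wrong. A crude comparison of proportions in a randomized trial is valid. This is one of several secondary endpoints in a Phase 2a study without multiplicity control, and the primary analysis already adjusts for baseline. Because the endpoint is a percentage fall from each subject's own baseline, much of the dependence on baseline may be gone before any adjustment. The SAP also tabulates baseline HAMD-17 by arm, so an imbalance would be seen. All of this stands, and it is why the point is only an improvement.

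Four stronger readings are tempting, and the documents do not support them:

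- A reader might infer that the response p-value is biased or its error rate inflated. It is not (step 3).
- A reader might infer that HAMD-17 response is singled out for crude analysis. That holds within the protocol. In the SAP, Section 7.4.7 also analyses CGI-I response by CMH with no named stratum, without the protocol's baseline CGI-S adjustment.
- A reader might blame the missing stratum for any divergence between the primary and response results. A shift of at most 0.2 standard errors for a 1-SD imbalance is a weak explanation, and dichotomizing alone can separate the two.
- A reader might take randomization to be certainly unstratified, or the unnamed stratum to be site. The documents are silent on strata and state neither.

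**Conclusion.** The point holds as a minor improvement. The HAMD-17 response test uses no named stratum although the obvious one is available for every analysed subject and a cut for it is already prespecified. The expected gain from stratifying is about 0 to 2 power points, with a rate-difference variance ratio of 0.98 to 1.00. It is near zero when response does not depend on baseline. The shift from a 1-SD imbalance is 0 to about 1.4 percentage points, and its direction depends on the slope.

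These sizes rest on assumed baseline SD, residual SD, slope and response rates. Entry is also filtered by a blinded rule list on clinical scales (Protocol 4.1.1), so the true baseline spread is unknown; a narrower spread shrinks the gain. Only a baseline-to-Week 8 relation stronger than the slope range assumed here gave a clearly larger gain.

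**What to change.** In Protocol Section 9.3.3.2 and SAP Section 7.4.7:

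- Stratify the HAMD-17 response CMH by baseline HAMD-17, <22 v ≥22, using the same baseline value as the primary MMRM.
- Report the Mantel-Haenszel stratified rate difference with its CI, so that estimate and p-value come from one analysis. Keep crude rates by arm as description.
- Give the SAP's CGI-I response CMH a baseline-severity stratum in the same way. The documents contain no CGI-S cut, so set one before unblinding or use the HAMD-17 cut.
- If a logistic or GEE model is preferred, report a standardized risk difference. Its odds ratio is conditional on baseline and would replace the planned effect measure.
- If the crude test is kept, say explicitly that no strata are used.

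The cost is a sentence or two in each document and one added term in the SAS call. No new data are needed, and type I error control is unaffected.
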